3.1. RATIONALE FOR DOSE

Results from the phase 1b COSMIC-021 study of cabozantinib in combination with atezolizumab in patients with previously untreated advanced renal cell carcinoma (RCC) were presented at the European Society for Medical Oncology (ESMO) 2018 Congress in Munich (68). This dose-escalation study primarily looked at the safety of cabozantinib + atezolizumab combination in untreated advanced RCC patients to determine the best dose to use in future clinical trials. The combination showed encouraging clinical activity in this group of patients, and the best dose of cabozantinib was found to be 40 mg in combination with the standard dose of atezolizumab (1200 mg/every 3 weeks) (68). Dosing selected for this trial is based in the aforementioned study.

4. HYPOTHESIS AND OBJECTIVES

4.1. STUDY HYPOTHESIS

The main hypothesis is that the administration of cabozantinib plus atezolizumab will improve the probability of expected objective response rate in advanced and refractory tumours of the endocrine system. This study will be considered positive if the main hypothesis is achieved in at least one cohort of patients.

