Simon-II optimal two-stage design was applied for sample size estimation. We hypothesize that the experimental therapy will improve the probability of expected objective response rate in refractory settings less than 5% in historical cohorts to 20% in the current study. With 80% of power (0.2) and unilateral alpha (0.1), 24 patients per cohort are needed to demonstrate the primary hypothesis. The Simon-II design suggested to observe ≥ 1 patient with objective response within the first 9 patients included in the first stage. If ≥ 1 out of 9 patients in each cohort achieve an objective radiological response in the first stage, study will continue recruiting 15 additional patients up to 24 patients per cohort. If ≥ 3 out of a total of 24 patients achieve a radiological objective response at the final analysis, the study should be declared positive. If stage I is reached only in one cohort, recruitment will continue in the successful cohort and stopped in the non-effective cohorts.

An overall description will be made of the variables included in the study. Absolute and relative frequency distributions (percentages) of qualitative variables will be presented, as well as measures of central tendency and dispersion (mean, standard deviation, median, minimum, and maximum values) of quantitative variables. The missing data will not be inputed and will be left as lost (missing value), however it will be presented.

The individual and summary on results of vital signs, ECG parameters, clinical laboratory data (haematology, serum biochemistry, and urinalysis) will be presented in tabular form. The values outside the reference range will be flagged. Clinically significantly abnormal values will be listed in tabular form. AEs will be tabulated by system organ class and preferred term after medical coding using the latest version of the NCI-CTCAE v5.0.

Main analyses populations:

- Intent-to-Treat (ITT)
- Per Protocol (PP)
- Safety population (SP)

INDEX

2. Introduction	19
2.1. Disease background	19
2.2. Systemic therapy for advanced and refractory tumours from endocrine system	22
3. Trial rationale	24
3.1. Rationale for dose	25
4. Hypothesis and Objectives	25
4.1. Study Hypothesis	25
4.2. Study Objectives	25
5. Study Design	25
5.1. Overall Study Design	25
5.2. Patient Screening	27
5.3. Patient Inclusion and Cohort Assignment	27
5.4. Patient Treatment	27
5.5. Patient Follow up After Treatment	27
5.5.1. End of treatment without progression	27

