1. Cabozantinib has shown promising activity, in several endocrine tumour types, including thyroid cancer, neuroendocrine tumours, as well as pheochromocytoma and paragangliomas (62-64). Cabozantinib increased PFS on progressive medullary thyroid cancer and refractory differentiated thyroid cancer patients with a manageable toxicity profile (62-63). Preliminary results in 10 pheochromocytoma patients showed an ORR of 40% and a clinical benefit rate of 90% (64).
2. The efficacy of anti-PD-1/PD-L1 treatments (as atezolizumab) in monotherapy seems to be limited to high grade tumours such as anaplastic thyroid cancers and MSI adrenocortical carcinomas. However, in most well-differentiated endocrine neoplasms, including thyroid and neuroendocrine tumours, the immune system plays a crucial role in the control of tumour growth without systemic therapies which allows the inclusion of active surveillance strategies in all treatment guidelines. Recent data showed potential higher activity, measured by ORR, of anti-PD1 monotherapy in well-differentiated neuroendocrine tumours of the lung than in gastroenteropancreatic origins (NTC03167853)(65).

3. The combination of cabozantinib and atezolizumab may be active in endocrine tumours by overcoming the resistance to prior antiangiogenic drugs and sensitising the tumours to immunotherapy through the combination of multikinase inhibitors and anti-PD-L1 therapy (66-67).

4.

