5. STUDY DESIGN

5.1. OVERALL STUDY DESIGN

This is an open labelled, single arm, multicohort phase II multicentre clinical trial of cabozantinib plus atezolizumab in advanced and refractory tumours from the endocrine system.

The dose scheme includes the initial dose of cabozantinib 40 mg qd + atezolizumab (1200 mg) intravenously

administered every 21 days (one cycle). Dose adjustment of cabozantinib is allowed as per the PI criteria but dose reductions of atezolizumab are not expected. Additional information on the treatment, modifications, and dose delays is available in section 7 of this protocol.

The CABATEN trial will include patients with advanced and refractory tumours of endocrine system (additional details on the eligibility criteria of the study are found in section 6 of this protocol) and patients would be allocated to six different cohorts according to the following tumour types:

- Cohort 1: Well-differentiated neuroendocrine tumours of the lung and thymus (WHO grades 1 and 2, typical and atypical carcinoids) after progression to somatostatin analogs, targeted agents, PRRT, and/or chemotherapy.
- Cohort 2: Anaplastic thyroid cancer in first-line or after progression to chemotherapy or investigational drugs.
- Cohort 3: Adrenocortical carcinoma after progression to chemotherapy and/or mitotane.
- Cohort 4: Pheochromocytoma and paraganglioma after progression to peptide receptor radionuclide therapy (PRRT) if indicated, prior chemotherapy and biological therapy, such as somatostatin analogs, are allowed.
- Cohort 5: Well-differentiated neuroendocrine tumours of digestive system (WHO grades 1 and 2) after progression to somatostatin analogs, targeted agents, PRRT, and/or chemotherapy.
- Cohort 6: Grade 3 neuroendocrine neoplasm (WHO grade 3, including NET and NEC G3) of any origin, excluding small cell lung cancer, after progression to chemotherapy or targeted agents/PRRT.

The design includes screening phase, treatment phase (including medical consultation and drug administration Q3w \pm 3 days), disease progression follow up by RECIST 1.1 every 12 weeks \pm 2w (disease progression assessments may be performed every Q8w \pm 2w if required by local standard clinical practice or by investigator criteria, as long as the frequency of the assessments is maintained), translational research with biopsies and blood samples and long term follow-up.

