10. STATISTICS

10.1. SAMPLE SIZE CALCULATION

Simon-II optimal two-stage design was applied for sample size estimation. We hypothesise that the experimental therapy will improve the probability of expected objective response rate in refractory settings, from less than 5 % in previous reports, to 20 % in the current study. With 80 % of power (0.2) and unilateral alpha (0.1), 24 patients per cohort are needed to demonstrate the primary hypothesis. The Simon-II design suggested the observation of ≥ 1 patient with objective response within the first nine patients included in the first stage. If ≥ 1 out of nine patients in each cohort achieve an objective radiological response in the first stage, the study will continue to recruit 15 additional patients up to 24 patients per cohort. If ≥ 3 out of a total of 24 patients achieve a radiological objective response at the final analysis, the study should be declared positive. If stage I is reached only in one cohort, recruitment will continue in the successful cohort and stopped in the non-effective cohorts.

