12.2. INDEPENDENT ETHICAL COMMITTEE (IEC) OR INSTITUTIONAL REVIEW BOARD (IRB) REVIEW

Prior to the commencement of the trial at a given site, this clinical trial protocol will be submitted together with its associated documents to the Central IEC for its approval, which will be filed in the Investigator Site File. A copy will be filed in the Sponsor Trial Master File.

The IEC will be asked to document the date of the meeting at which the favourable opinion or approval was given, with the members and voting members present. Written evidence of favourable opinion or approval that clearly identifies the trial, the clinical trial protocol and the version, the Subject Information and Informed Consent Form, should be provided.

Amendments to this clinical trial protocol will also be submitted to the concerned IEC or IRB, before implementation of substantial changes. Relevant safety information will be submitted to the IEC during the course of the trial, in accordance with national regulations and requirements.

Initial IEC positive vote, and all materials approved by the IEC for this study including the patient consent form and recruitment materials must be maintained by the Investigator and made available for inspection.

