2.5.1. PRIMARY EFFICACY ANALYSIS

Overall Response Rate (ORR): includes patients with confirmed partial (PR) and complete response (CR) as best response according to RECIST v 1.1.

The ORR is the proportion of patients with tumor size reduction (CR or PR), recorded between the date of the first dose and the last tumor evaluation before starting a subsequent treatment of each patient in the study. The proportion of response rates will be expressed with the 95% confidence interval.

The Overall response rate by RECIST in the ITT population (n=XX) is shown in the following table:

Table 176. ORR (ITT)

	Cohort 1 N (%), CI95%	Cohort 2 N (%), CI95%	Cohort 3 N (%), CI95%	Cohort 4 N (%), CI95%	Cohort 5 N (%), CI95%	Cohort 6 N (%), CI95%
ORR						
CR						
PR						
SD						
PD						
Total	n (100%)					
CR or PR						
SD or PD						
Total	n 100%	n (100%)				

The Overall response rate by RECIST in the PP population (n=XX) is shown in the following table:

Table 177. ORR (PP)

	Cohort 1 N (%), CI95%	Cohort 2 N (%), CI95%	Cohort 3 N (%), CI95%	Cohort 4 N (%), CI95%	Cohort 5 N (%), CI95%	Cohort 6 N (%), CI95%
ORR						
CR						
PR						
SD						
PD						
Total	n (100%)					
CR or PR						
SD or PD						
Total	n 100%	n (100%)				

Sponsor: Grupo Español de Tumores Neuroendocrinos y Endocrinos (GETNE)

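### The protocol calls the whole study positive if any one of six cohorts passes, but never gives that rule's error, which reaches 44% if every cohort has a true response rate of 5%

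*Combined protocol and SAP*

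**What the plan says.** Protocol 4.1 gives the study-level criterion: "This study will be considered positive if the main hypothesis is achieved in at least one cohort of patients". Protocol 5.1 says that "patients would be allocated to six different cohorts according to the following tumour types".

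The error rate and power are set in protocol 10.1, and SAP 1.4.1 repeats the text: "With 80 % of power (0.2) and unilateral alpha (0.1), 24 patients per cohort are needed to demonstrate the primary hypothesis". The hypothesised change in response rate is "from less than 5 % in previous reports, to 20 % in the current study". A cohort continues past its first nine patients if at least one responds, and passes if at least 3 of 24 respond. Each cohort continues or stops on its own result.

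The synopsis, protocol 10.1 and SAP 1.4.1 all say that if at least 3 of 24 patients "achieve a radiological objective response at the final analysis, the study should be declared positive". In context this describes one cohort's result, but the word used is study.

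SAP 2.5.1 reports the response rate by cohort in Tables 176 and 177: "The proportion of response rates will be expressed with the 95% confidence interval". The SAP does not repeat the rule in 4.1. Neither document gives a type I error for that rule, adjusts for multiplicity, or says that no adjustment is intended.

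**The concern.** Two claims share the word positive. One is about a cohort and carries a one-sided error of 10%. The other is about the study, and succeeds if any of six such tests succeeds. A reader who meets a positive study next to an alpha of 0.1 may take 10% as the error of the study verdict. The wording in the synopsis, 10.1 and SAP 1.4.1, which attaches the study verdict to a cohort's 3-of-24 rule, encourages that reading.

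What is at stake is the prespecified headline. If the combination were inactive in every tumour type, the trial could still be called positive far more often than 1 time in 10, and nothing in the plan warns of it.

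**Working it through.** **Inputs.** Six cohorts (protocol 5.1). Null response rate 5% (stated as below 5%), target 20%, one-sided alpha 0.10, power 80%; 9 then 15 patients, continue on at least 1/9, pass on at least 3/24 (protocol 10.1, SAP 1.4.1). Success in any one cohort suffices (protocol 4.1).

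**Step 1: reproduce the cohort design.** For true response rate p, with X1 ~ Bin(9, p) and X2 ~ Bin(15, p),

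P(pass) = Σ over x ≥ 1 of P(X1 = x) × P(X2 ≥ 3 − x).

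At p = 0.05:

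- x = 1: 0.29854 × 0.17095 = 0.05104
- x = 2: 0.06285 × 0.53671 = 0.03373
- x ≥ 3: 0.00836 × 1 = 0.00836
- Sum: 0.0931

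At p = 0.20 the same sum is 0.8047. A full search for the Simon optimal design with these inputs returns the stated design (stop at 0/9, fail at 2/24 or fewer). The plan's cohort figures are therefore correct.

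**Step 2: error of the rule in 4.1.** Cohorts contain different patients, so they are treated as independent. With a common true rate and no active cohort,

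P(at least one of six passes) = 1 − (1 − P(pass))^6.

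| Common true response rate | P(pass), one cohort | Any of six |
|---|---|---|
| 2% | 0.0093 | 5.4% |
| 3% | 0.0270 | 15.2% |
| 4% | 0.0552 | 28.9% |
| 5% | 0.0931 | 44.4% |

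At 5%: 1 − (1 − 0.0931)^6 = 0.444. The any-of-six error equals 10% at a common rate of about 2.5%.

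**Step 3: a mixed null.** With three cohorts at 5% and three at 2%: 1 − (1 − 0.0931)^3 × (1 − 0.0093)^3 = 0.275.

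**Step 4: if one cohort is truly active.** The trial rationale (protocol section 3) reports a 40% response rate in 10 pheochromocytoma patients given cabozantinib, that is 4/10, exact 95% CI 12.2% to 73.8%. The probability that cohort 4 alone makes the study positive is:

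- 99.0% if its true rate is 40%
- 80.5% if it is 20%
- 48.7% if it is 12.2%

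**Step 5: would a stricter cut-off cure it?** Keeping the 1/9 rule:

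| Final cut-off | Cohort error at 5% | Any of six at 5% | Cohort power at 20% |
|---|---|---|---|
| ≥ 3/24 | 9.3% | 44.4% | 80.5% |
| ≥ 4/24 | 2.6% | 14.8% | 68.9% |
| ≥ 5/24 | 0.6% | 3.3% | 51.8% |

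**The case against.** The strongest reply is that nothing operational depends on the label. The rule appears only in 4.1; continuation is decided by cohort, the primary tables report by cohort, and no dosing, enrolment or analysis step follows from it. The trial is titled exploratory, and separate cohort tests without adjustment are a recognised choice in a basket design. This is right about per-cohort testing, and no adjustment is asked for. It does not cover the single verdict that 4.1 adds on top.

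Second, 44% is the maximum under the null: it needs all six tumour types at exactly 5%, and the pheochromocytoma result makes that doubtful for cohort 4. This is true, and the lower figures belong beside it. But 5% is also where the plan's own alpha is met. If cohort 4 is active, the verdict is usually true but says nothing about the other five tumour types.

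Third, the planned intervals protect the reader. They do in part: a bare pass at 3/24 has an exact 95% CI of 2.7% to 32.4%, which includes 5%. It also means the label and the interval can point in different directions.

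Fourth, the calculation assumes that every continuing cohort reaches 24. The tumours are rare, and withdrawn patients are not replaced (protocol 6.3). As an illustration, suppose two of the six cohorts could reach only 15 patients with the bar still at 3 responses. Their P(pass) at 5% falls to 0.0348, and the any-of-six figure to 1 − (1 − 0.0931)^4 × (1 − 0.0348)^2 = 37%. This qualifies the number without removing the point.

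**Conclusion.** The concern holds. The cohort design is correct, and its 10% error is honoured within each cohort. The study-level rule in 4.1 has no stated error, and with no active cohort that error exceeds 10% once the common true response rate is above about 2.5%, reaching 44.4% at 5%. These figures assume independent cohorts, a common true rate, full accrual, and the stage 1 stop applied as written. This should be fixed: it does not change patient management or the cohort analyses, but it determines what the prespecified headline can support.

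**What to change.** **Preferred.** Draw conclusions cohort by cohort. Delete the study-level rule in 4.1. In the synopsis, protocol 10.1 and SAP 1.4.1, say that the cohort, not the study, is declared positive at 3 or more of 24.

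**Lighter option.** Keep the rule in 4.1 and state its error beside it.

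**In either case,** add to protocol 10.1 and SAP 1.4.1:

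> Type I error is controlled at one-sided 10% per cohort only. If all six cohorts have a true response rate of 5%, the probability that at least one is declared positive is 44% (independent cohorts, full accrual); it is lower if the true rates are lower.

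Do not tighten the cut-off. At 4/24 the any-of-six error is still 14.8%. At 5/24 it falls to 3.3%, but cohort power drops to 51.8%.

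**Cost.** This is a wording amendment. Removing a success criterion from a running trial may count as substantial, and protocol 12.2 says: "Amendments to this clinical trial protocol will also be submitted to the concerned IEC or IRB, before implementation of substantial changes". The disclosure sentence alone is the smaller change. The sponsor loses, or has to qualify, a single positive-study headline. Sample size, cut-offs and within-cohort power are unchanged.

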4.2. STUDY OBJECTIVES

Primary objective:

- To assess the efficacy of cabozantinib plus atezolizumab by means of radiological objective response rate (ORR) as per RECIST V1.1, in advanced endocrine tumours.

Secondary objectives:

- To evaluate the safety profile of cabozantinib and atezolizumab combination, according to NCI-CTCAE V5.0.
- Duration of response (DoR) as per RECIST V1.1.
- Progression-free survival (PFS): median PFS as per RECIST V1.1.
- Overall Survival (OS): median OS as per RECIST V1.1.
- Tumour biomarkers: translational substudy (optional).
- Quality of Life (QoL).

Study endpoints for these objectives are described in section 10.2 of this protocol.

5. STUDY DESIGN

5.1. OVERALL STUDY DESIGN

This is an open labelled, single arm, multicohort phase II multicentre clinical trial of cabozantinib plus atezolizumab in advanced and refractory tumours from the endocrine system.

The dose scheme includes the initial dose of cabozantinib 40 mg qd + atezolizumab (1200 mg) intravenously

administered every 21 days (one cycle). Dose adjustment of cabozantinib is allowed as per the PI criteria but dose reductions of atezolizumab are not expected. Additional information on the treatment, modifications, and dose delays is available in section 7 of this protocol.

The CABATEN trial will include patients with advanced and refractory tumours of endocrine system (additional details on the eligibility criteria of the study are found in section 6 of this protocol) and patients would be allocated to six different cohorts according to the following tumour types:

- Cohort 1: Well-differentiated neuroendocrine tumours of the lung and thymus (WHO grades 1 and 2, typical and atypical carcinoids) after progression to somatostatin analogs, targeted agents, PRRT, and/or chemotherapy.
- Cohort 2: Anaplastic thyroid cancer in first-line or after progression to chemotherapy or investigational drugs.
- Cohort 3: Adrenocortical carcinoma after progression to chemotherapy and/or mitotane.
- Cohort 4: Pheochromocytoma and paraganglioma after progression to peptide receptor radionuclide therapy (PRRT) if indicated, prior chemotherapy and biological therapy, such as somatostatin analogs, are allowed.
- Cohort 5: Well-differentiated neuroendocrine tumours of digestive system (WHO grades 1 and 2) after progression to somatostatin analogs, targeted agents, PRRT, and/or chemotherapy.
- Cohort 6: Grade 3 neuroendocrine neoplasm (WHO grade 3, including NET and NEC G3) of any origin, excluding small cell lung cancer, after progression to chemotherapy or targeted agents/PRRT.

The design includes screening phase, treatment phase (including medical consultation and drug administration Q3w \pm 3 days), disease progression follow up by RECIST 1.1 every 12 weeks \pm 2w (disease progression assessments may be performed every Q8w \pm 2w if required by local standard clinical practice or by investigator criteria, as long as the frequency of the assessments is maintained), translational research with biopsies and blood samples and long term follow-up.

Study treatment will begin as soon as possible after signing the informed consent (as per section 5.2 of this protocol) and inclusion will be completed as per section 5.3 of this protocol.

The first administration of cabozantinib will be carried out after the infusion of the first atezolizumab cycle, the patient will take the treatment in the presence of a member of the Site staff who will advise the patient on the correct intake of the treatment (according to the indications of the section 7.1 of this protocol), discuss with the patient the process of completing the patient diary, and address the doubts that the patient may have at the time. In addition, patient must bring all medication bottle(s) (including empty ones) to each visit, for IMP adherence and compliance traceability purposes.

After the first supervised administration, cabozantinib will be self-administered by patients daily according to the indications of the Investigator staff and as indicated in section 7 of this protocol. Treatment with cabozantinib will be continuous until the progression of the disease and/or unacceptable toxicity, among others. Patients will attend follow-up visits with the study doctor every 3 weeks for clinical assessment, laboratory tests, laboratory determinations should be made within 72 hours prior to the date of administration of atezolizumab, in order to assess the relevance of administration of a new cycle (modifications, delays, etc.), according to what is specified in sections 7.1.2 and 7.2.2. Additionally, the study doctor may request patients to come to the centre more frequently in case of toxicity or discomfort of the patient. Additional information about the study's determinations is found in section 8 of this protocol.

Treatment and study determinations will be the same for all the patients, regardless of the cohort in which the patients are included.

This is a study with Simon's two-stage design; it requires that an event is observed in the first nine patients before continuing to the second stage where there is a possible inclusion of 15 additional patients (up to a maximum of 24 patients per cohort).

In addition, an optional biomarker study with tumour and blood samples will be performed (if it is feasible for the Sponsor), and it is detailed in the corresponding biological samples manual.

